2.3 Study population

Adults or children in community setting with RAT or PCR-confirmed SARS-CoV-2 infection and their household contacts. All participants who enter the trial based on a positive RAT will have a confirmatory PCR test taken prior to commencing study medication. This is referred to as the Day 1 swab. Only participants who test PCR negative to SARS-CoV-2 on day 1 swab contribute to the primary outcome measure in addition to relevant secondary aims. Anyone testing PCR positive on day 1 contributes to relevant secondary aims only.

A household contact is defined as anyone living in the same house (street address) regardless of their direct biological relationships.

Children (<5 year old) in households are not treated but monitored only. For households in which the child is the index case, only household contacts >5 years age are randomised to treatment. For households in which the index case is an adult, and the child <5 years old tests PCR negative on day 1, then the child contribute to primary and secondary outcomes even though they themselves are not treated.

Inclusion criteria:

- Any person > 5 years of age who tests positive to SARS-CoV-2 or is a household contact of someone of any age who tests positive is eligible for the trial.
- Index case must be within 72 hours of positive test.
- The positive test can be a RAT or a standard PCR nasal swab performed at a National Association of Testing Authorities (Australia) (NATA) accredited laboratory for the diagnosis of COVID-19 as per the department of health regulations. If initial test is a RAT, then a standard PCR nasal swab performed at a NATA accredited laboratory for the diagnosis of COVID-19 as per the department of health regulations will be collected prior to commencement of study medication but does not delay entry into the study awaiting the confirmatory result.
- All participants must provide a signed and dated consent form and for children < 16 years have a legally acceptable representative capable of understanding the informed consent document and providing consent on the participant's behalf. Consent forms will be developed in multiple languages and provided in a language that the participants are fluent in speaking.
- At least one other person other than the index case in each household must consent to participation to enable the consenting members of the household to be randomised. Household members who do not consent to participate in the randomised trial but who consent to have their COVID-19 status recorded can contribute to outcome measures where relevant.

Exclusion criteria:

- Children age < 5 years are excluded from being randomised to therapy but can contribute to the outcome measures if they are swab negative on day 1.
- Documented Heparin allergy
- Previous documented heparin induced thrombocytopenia (HIT)
- Recurrent epistaxis that has required hospitalisation in last 3 months
- >72 hours since index case tested positive
- Inability to provide participant information and consent form and study instructions in a language in which the patient is competent.

2.4 Intervention

Unfractionated heparin (UFH) 1400u each nostril (as heparin solution 5,000u/ml, 140microL/actuation, TWO actuations each nostril) THREE times daily via a plastic nasal inhalator device (Aptar, UK) for 10 days. This is a maximal dose per day of UFH of 8400u, 700 x 2 actuations per nostril (1400 x2) 3 times per day (1400x2x3 = 8400u).

Comparator 0.9% saline (as saline solution, 140 microlitres/actuation, TWO actuations each nostril) THREE times daily via a plastic nasal inhalator device (Aptar, UK) for 10 days.

2.5 Randomisation and blinding

An independent statistician prepared the randomisation list using block randomisation. This list was provided directly to Northern Health pharmacy. Once a household was enrolled, the pharmacy was notified directly and prepared and dispensed the required study drug based on the randomisation schedule. The randomisation was stratified by randomised within 48 hours of positive test done by the participant for the index case (time of test being collected) versus those who were randomised between 48 and 72 hours, and by whether or not the index case is a child < 5 years.

The randomisation was a 1:1 randomisation by household. If the index case and at least one other person in the household were eligible and consented then all consenting and eligible participants within that household were randomised to the same arm of the study, either active treatment or comparator.

This is a double blind trial and both participants and researchers will be blinded throughout the study. The bottles distributed to the patients were listed as trial medication and the active comparator and placebo are both colourless, odourless and tasteless packaged in similar looking bottles. Both active drug and comparator are stable at room temperature and need no specific storage requirements.

2.6 Sample size

For the primary research outcome, a sample size of 120 index cases per arm will provide 80% power. We anticipate that the attack rate for within household transmission will be approximately 85% in the control arm and 75% in the intervention arm. Under these assumptions, in a cluster randomised trial with a binary outcome, assuming an intracluster correlation coefficient of 0.2, an alpha of 0.05 (two sided), and assuming 3 additional household members (in addition to the index case) we have 80% power to detect a reduction in transmission to household contacts. The requisite sample size is then 120 index cases and 360 household contacts per arm. Allowing for 10% loss to follow-up this is increased to 134 index cases (households) per arm, approximately 536 persons per arm. We plan to enroll 268 households and approximately 1072 individuals.

If the household size is 2 additional people, rather than 3, and with all other assumptions the same, we would require 334 households and approximately 1002 individuals. The target sample size for the primary outcome is 1100 individuals enrolled.

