3.4. Definition of analysis populations

Different study populations are defined to address the different research questions. These are:

- All household members of households where at least one person tested positive and at least one person tested negative for SARS-CoV-2 on day 1 on PCR testing. This includes children < 5years old who test negative to SARS-CoV-2 on day 1.
- All household members who test negative for SARS-CoV-2 on day 1 (including children < 5 years old) on PCR testing.
- All household members (index cases and household contacts) who test positive for SARS-CoV-2 on day 1 on PCR testing. This excludes children < 5 years old who test positive to SARS-CoV-2 on day 1.
- All household members (index cases and household contacts; 5 years and older) prescribed study drug, regardless of SARS-CoV-2 infection status
- All enrolled participants, regardless of SARS-CoV-2 status, who received at least one dose of study drug. This excludes children < 5 years.
- All enrolled participants, regardless of SARS-CoV-2 status.

In Sections 5 and 6 we specify which population is used to assess each of the study objectives. Despite the specific analysis populations described, all analyses will follow the Intention to treat (ITT) principle where participants will be analysed in the arms they were randomised to, regardless of whether they received or used study drug.

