5. ANALYSIS OF THE PRIMARY OUTCOME(S)

5.1. Main analysis

The primary outcome will be the number (and proportion) of household members swab negative on day 1 (study timepoint called baseline) testing positive for SARS-CoV-2 by PCR on either of three routine nasopharyngeal swabs on day 3, 5 and 10 after enrolment.

Primary estimand

Population: Household members (including children < 5 years) who test negative for SARS CoV-2 on day 1 (baseline) PCR testing using the health care provider swabs

Treatment: Initially randomised intervention to unfractionated intranasal heparin 1400u each nostril (as heparin solution 5,000u/ml, 140microL/actuation, TWO actuations each nostril) THREE times daily via a plastic nasal inhalator device or saline control and any subsequent deviations to the per protocol use of the intervention over 10 days

Outcome: Testing positive for SARS-CoV-2 by PCR on any of three health care provider collected swabs at days 3, 5 and 10. The algorithm to determine SARS-CoV-2 positivity is described in detail in Section 3.8. If one of the post-baseline swabs is missing, but all observed swabs were negative, the participant will be regarded to be negative. If more than one post-baseline swab is missing and the observed swabs were all negative, the outcome will be regarded to be missing.

Summary measure: Both relative (risk ratio) and absolute differences (risk difference) in proportions will be reported with 95% confidence intervals

Potential intercurrent events:

Index case in the household not taking study drug. This is defined as compliance <90% Participant (this household member) not taking study drug. This is defined as compliance <90% Either participant (this household member) or index case stop treatment due to adverse event Participant hospitalisation during first 10 days (removed from household) Participant received an anti-viral

Strategy for handling intercurrent event:

In the primary analysis all intercurrent events will be handled through the treatment policy strategy, which means that the intercurrent events will be ignored.

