The analysis will follow the intention to treat principle, but only some households will be eligible for this objective. A household will be eligible if there is at least one participant in the household who tested positive to SARS-CoV-2 by PCR on Day 1 and one participant who tested negative to SARS-CoV-2 by PCR on Day 1, using the health care provider collected swab. It does not matter whether it was the index case or another household member who tested positive. Households where all participants test positive or where all participants test negative will not be eligible for this analysis.

Treatment arms will be compared using generalised linear mixed models (GLM) with infection status as the binary outcome, adjusting for stratification factors (time from positive test to randomisation, whether the index case is a child < 5 years), participant age, inhaled steroid use at baseline, days since symptom onset at randomisation, whether there are children in the household and household size (referred to as the defined baseline covariate set, see Section 3.9), with household as random effect to take the clustering by household into account. Both relative and absolute differences in proportions will be reported with 95% confidence intervals.

Relative differences (risk ratios) between the treatment arms will be calculated using a Poisson regression with robust standard errors in Stata as follows:

xtpoisson outcome i.arm baseline_covariates, re vce(robust) irr

Absolute differences (risk difference) between the treatment arms will be calculated in Stata as follows using a mixed effects GLM with random intercepts: megIm outcome i.arm baseline_covariates || household:, family(bin) link(logit)

The margins statement will be used to compute the risk difference by subtracting the probability of the outcome in the control arm from the probability in the treatment arm margins i.arm, atmeans post lincom _b[1.arm] - _b[0.arm]

Both these models are fairly complicated models to fit and might not converge if sparse data is encountered, given all the baseline covariates included. If the models do not converge, the following strategies will be tried:

- Exclude some of the baseline covariates especially binary covariates, covariates with sparse categories, or covariates with little variability
- Or, fit the following simpler models

Relative differences (risk ratios) between the treatment arms will be calculated in Stata as follows using robust standard errors:

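### The 80% power in SAP Section 2.6 counts every household contact, but the primary analysis keeps only day 1 PCR-negative members of mixed households

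*SAP*

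**What the plan says.** SAP Section 2.6 states its planning rates as follows: "We anticipate that the attack rate for within household transmission will be approximately 85% in the control arm and 75% in the intervention arm". With an ICC of 0.2, a two-sided alpha of 0.05, 80% power and three contacts per index case, it concludes: "The requisite sample size is then 120 index cases and 360 household contacts per arm". The only inflation follows: "Allowing for 10% loss to follow-up this is increased to 134 index cases (households) per arm". That makes 268 households and about 1072 people. A variant with two contacts per household needs 334 households. The section closes with "The target sample size for the primary outcome is 1100 individuals enrolled".

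The primary analysis is narrower:

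- Section 2.3: "Only participants who test PCR negative to SARS-CoV-2 on day 1 swab contribute to the primary outcome measure".
- Section 5.1, population of the primary estimand: "Household members (including children < 5 years) who test negative for SARS CoV-2 on day 1 (baseline) PCR testing".
- Section 5.1, household eligibility: "Households where all participants test positive or where all participants test negative will not be eligible for this analysis".

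Section 3.4 also defines a population for the secondary outcomes, "All household members (index cases and household contacts) who test positive for SARS-CoV-2 on day 1 on PCR testing", so the plan expects some contacts to be positive already on day 1.

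**The concern.** Section 2.6 and Section 5.1 count different people. The sample size treats every contact as analysed. The estimand removes contacts already positive on day 1, and the eligibility rule removes whole households that are all positive or all negative. These exclusions are built into the design and are separate from loss to follow-up, so the 10% allowance does not cover them.

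Section 2.6 also leaves open whether 85% and 75% are the risks among contacts negative on day 1 or the attack rates over all contacts, including those infected before treatment starts. The two readings move power in opposite directions. If the trial finds no difference, a reader who wants to know what it was able to detect cannot work that out from the stated inputs.

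**Working it through.** **Inputs.** From SAP Section 2.6: 85% vs 75%, ICC 0.2, two-sided alpha 0.05, 80% power, 3 (or 2) contacts per household, 10% loss, target 1100. Allocation is 1:1 by household (Section 2.5). The share f of contacts who are PCR negative on day 1 is not in the SAP; it is an assumption, shown over a range.

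**Reproducing the plan's figures.** The two-proportion formula with pooled variance under the null gives, per arm under individual randomisation,

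n = [1.96 × √(2 × 0.80 × 0.20) + 0.8416 × √(0.85 × 0.15 + 0.75 × 0.25)]² / 0.10² = 250.

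- Three contacts: design effect 1 + 2 × 0.2 = 1.4; 250 × 1.4 = 350 contacts, or 117 households per arm (SAP: 360 and 120). Power with 120 × 3 is 81%.
- Loss: 120 / 0.9 = 133.3, rounded up to 134 (SAP: 134).
- Two contacts: design effect 1.2; 250 × 1.2 / 2 = 150 households per arm; 150 / 0.9 rounds up to 167; × 2 = 334 (SAP: 334).

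The arithmetic is sound for its inputs. It matches only when every contact is analysed and 10% loss is the sole allowance.

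**Applying the day 1 restriction.** Let k be the number of day 1-negative contacts in a household, k ~ Binomial(3, f). The effective sample size per arm is

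n_eff = H × Σ P(k) × k / (1 + (k − 1) × 0.2), with H = 120 followed-up households.

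*Reading A: 85% vs 75% are the rates among day 1 negatives.*

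| f | Contacts analysed per arm | n_eff | Power | Difference from 85% detectable with 80% power |
|---|---|---|---|---|
| 1.0 | 360 | 257 | 81% | 9.9 points |
| 0.9 | 324 | 239 | 78% | 10.2 points |
| 0.8 | 288 | 220 | 75% | 10.7 points |
| 0.7 | 252 | 199 | 70% | 11.3 points |
| 0.5 | 180 | 152 | 59% | 13.2 points |

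Power crosses 80% at f = 0.96.

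Variants on Reading A, at f = 0.9, 0.8 and 0.7:

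- Target of 1100: 1100 / 4 / 2 × 0.9 = 123.75 households per arm; power 79%, 76%, 72%, crossing 80% at f = 0.92.
- Two contacts, 150 households per arm: 77%, 72%, 67%.
- Day 1 positivity removing whole households (n_eff = 120 × f × 3 / 1.4): 77%, 72%, 66%.

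*Reading B: 85% vs 75% are rates over all contacts, with day 1 positives counted as infected and unaffected by treatment.* The rates in the analysed set are then (0.85 − (1 − f)) / f and (0.75 − (1 − f)) / f.

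| f | Control rate | Heparin rate | Power |
|---|---|---|---|
| 0.9 | 83% | 72% | 83% |
| 0.8 | 81% | 69% | 86% |
| 0.7 | 79% | 64% | 89% |

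At f = 0.7 the same text supports a power of 70% or of 89%.

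**The case against.** The strongest reply is that no calculation in Section 2.6 is wrong and that a loss of power is not established. The section speaks of an attack rate for transmission within households and never mentions day 1 status, which fits Reading B at least as well as Reading A; on Reading B the trial is conservatively sized. This stands as far as direction goes: the SAP does not show that power is lost. It does not rescue the stated figure, because on Reading B the rates compared in the primary analysis differ from the planning rates.

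Second, f is unknown and the effect is modest near f = 0.9: the detectable difference is 10.2 points against the planned 10, and with an ICC of 0.15 (an assumption) power there would be 81%. That is fair. At f = 0.7 or lower on Reading A the loss is material.

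Third, some features offset the loss. A PCR-negative index case can enter the primary set if another household member is positive, and Section 2.3 lets non-consenting members whose status is recorded contribute where relevant. Their numbers are unknown, and Section 2.6 does not count them either. The 1100 target adds only 28 people to 1072, about seven households of four.

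Fourth, Section 4.1 already plans to report eligible households and positive and negative members, and a null result should be read mainly from its confidence interval. Both points are right, but neither makes the stated 80% apply to the analysed set.

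**Conclusion.** The concern holds. The 80% in Section 2.6 describes an analysis of all contacts, which is not the primary analysis defined in Sections 2.3 and 5.1. The fault lies in a mismatch of populations and an unstated definition of the planning rates; the arithmetic itself is correct.

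Its size depends on two things the SAP does not give: f, and the population to which 85% and 75% apply. For f between 0.9 and 0.7, power with 120 households per arm runs from 78% down to 70% on Reading A and from 83% up to 89% on Reading B. These figures keep the ICC at 0.2, take day 1 status as independent between contacts within a household unless stated otherwise, and leave out PCR-negative index cases and households with no positive member. The estimand and the analysis model are unaffected. What suffers is the interpretation of the stated power.

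**What to change.** Restate Section 2.6 for the primary analysis population:

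1. Say whether 85% and 75% refer to contacts PCR negative on day 1 or to all contacts. If all contacts, give the implied rates among day 1 negatives.
2. Give the expected number of eligible households and day 1-negative contacts, or the observed number pooled over arms and blinded to allocation.
3. State the resulting power, or the difference detectable with 80% power, at the planning rates and ICC.

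The cost is SAP wording only. No added enrolment and no change to the estimand or model is needed, though the restated power may be less favourable than 80%.

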2.7 Study procedures

When a participant is confirmed to be SARS-CoV-2 positive all consenting household members are enrolled and randomised to the same treatment arm. All consenting household members 5 years of age and older will be given the same study treatment. Treatment is 10 days and follow up for primary outcome is 10 days. Follow up for some secondary outcomes are 28 days and outcomes related to long COVID is 6 and 12 months post randomisation.

Daily communication via SMS, online or phone will be conducted by a research team member who will be trained in standard operating procedures as per trial manual. Paediatric or adult swabs (Rhinomed) will be provided to all participants with detailed instructions for self-collection and storage until collected by a research team member. Health care provider collected PCR nasopharyngeal swabs will be collected from all participants prior to commencement of study medication and on day 3, 5 and 10 (+/- 1 day for all time points).

Phone call follow up at day 14 and 28 by a research team member will assess which participants became symptomatic after the initial treatment period and whether participants required hospitalisation during that time. Detailed medical information as to reasons for hospital admission will be sought to confirm if admission was related to COVID-19 infection or for alternative reasons. Research team members will be trained specifically in questions to ask according to trial manual, which will include an escalation process if a research team member believes that additional clinical care is required for the participant or family member.

Telemedicine follow up at day 180 +/- 10 days and day 365 +/- 10 days to ascertain any evidence of long COVID neurological symptoms.

2.8 Deviations from protocol

Secondary measures 1.5 and 1.6 were not specified in the protocol, but were added to the statistical analysis plan.

Reference to consecutive daily swabs were removed, since only the healthcare provider swabs are used and they are not collected daily.

No other large deviations from the protocol occurred. Where the text deviates from the protocol, the changes were made to resolve inconsistencies and ambiguities, without the intention of diverging from the original protocol.

Full details of the background to the trial and its design are presented in the protocol.

3. GENERAL STATISTICAL METHODOLOGY

3.1. Objectives of analysis plan

This statistical analysis plan described the planned analyses of the primary and secondary objectives of the INHERIT trial protocol in detail. Additional post hoc analyses are not included.

3.2. Analysis software

Stata version 18.0 or later will be used to analyse the data.

3.3. Definition of baseline

Baseline is defined as day 1 PCR and pre-Day 1 measures for other measures. Only measures taken prior to dispending study drug will be used as baseline measures.

3.4. Definition of analysis populations

Different study populations are defined to address the different research questions. These are:

- All household members of households where at least one person tested positive and at least one person tested negative for SARS-CoV-2 on day 1 on PCR testing. This includes children < 5years old who test negative to SARS-CoV-2 on day 1.
- All household members who test negative for SARS-CoV-2 on day 1 (including children < 5 years old) on PCR testing.
- All household members (index cases and household contacts) who test positive for SARS-CoV-2 on day 1 on PCR testing. This excludes children < 5 years old who test positive to SARS-CoV-2 on day 1.
- All household members (index cases and household contacts; 5 years and older) prescribed study drug, regardless of SARS-CoV-2 infection status
- All enrolled participants, regardless of SARS-CoV-2 status, who received at least one dose of study drug. This excludes children < 5 years.
- All enrolled participants, regardless of SARS-CoV-2 status.

In Sections 5 and 6 we specify which population is used to assess each of the study objectives. Despite the specific analysis populations described, all analyses will follow the Intention to treat (ITT) principle where participants will be analysed in the arms they were randomised to, regardless of whether they received or used study drug.

